## **Study protocol**

**Participants:** We aim to recruit a total of 120 participants (60 for the intervention and 60 as a control group).

Inclusion criteria include any gender, age between 40 and 89 years old, illiteracy (TOFHLA score <53) and availability to participate in the study for at least 12 months.

Exclusion criteria will be: A) Presence of remarkable cognitive complaints and/or decompensated psychiatric illness (depression and anxiety) and/or current substance abuse such as alcohol and illicit drugs use. B) Objective cognitive impairment: 2 standard deviations or less for age and education on the Mini-Mental State Evaluation (MMSE) and/or 6 or less points on the delayed recall task from the Brief Cognitive Battery. C) History of previously diagnosed dyslexia D) Formal MRI contraindications including metal or claustrophobia. E) Severe structural lesions detected by MRI.

Informed consent will be written in accessible language and collected using the approach “teach-to-goal developed for vulnerable populations.

First, we will do pair matching with the 120 participants dividing them into two clusters paired for age, sex and baseline non-verbal intelligence and literacy level (by TOFLHA). Next, within each pair, one cluster is randomized to receive the intervention (n=60), and the other cluster receives the placebo (n=60). Based on our pilot project and historical data, we calculate an attrition rate of 20%. Thus, the final sample is expected to have 96 individuals. We will reassess the participants’ cognition and neuroimaging after 6 months.

**Literacy and cognitive reserve assessment:** Reading comprehension and numeracy skills will be evaluated using the Test of Functional Health Literacy in Adults (TOFHLA) that has been validated for Brazilian Portuguese. A score of or lower 53 defines illiteracy. Global cognitive reserve will be assessed with a structured questionnaire available in Portuguese, that includes years of education, leisure activities and occupational attainment. Sociodemographic features, the level of physical exercise, smoking, and alcohol habits, as well as the presence of psychiatric illness, will be addressed with specific questionnaires.

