**Literacy training (intervention):** The basic-literacy training will be given for 6 months. At baseline, participants will be randomized into four classes of 30. Co-I [name], who is an expert in adult education, will oversee the classes and meet the teachers periodically, and each class will count with a certified and experienced lead teacher and teacher aid. Two of the classes of 30 each will be the intervention group. They will receive literacy training based on analytical and phonemic methods for enabling reading and writing. The two other classes of 30 each will be the placebo group. The placebo group will have access to non-literacy classes offered at the adult school, including geography, history, informatics, and sciences, but no literacy-training.

Both the intervention and the placebo groups will attend classes of two hours/day for four days/week. The teachers will record attendance. The follow-up neuroimaging and neuropsychology testing will be done at the 6 months mark. The informed consent will have a session explaining that participants will be randomly assigned to participate in the intervention or placebo group in the first 6 months so that they will be blind to which group they were assigned for at baseline. Based on the literacy-program experience, we expect a dropout rate of 20%. Thus, we expect to have 96 participants concluding the study. Participants who drop out will be monitored by phone calls every three months and will be also reassessed after 6 months, if interested. We will compare the dropout group with the groups that kept the training to see whether there were differences in intelligence or sociodemographic aspects.

**Blood samples:** At the baseline, we will collect blood samples of participants to assess the apolipoprotein E genotype. Upon participant consent, plasma and serum samples will be stored for future analysis of potential peripheral markers associated with cognitive reserve.

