Better Memory with Literacy Acquisition Later in Life

NCT number NCT04473235

Date April, 29th 2024

Statistical analysis plan

Primary outcome:

The episodic memory will be measured using the Free and Cued Selective Reminding test (FCSRT). This test has 3 steps. First, the participant learns 16 figures, 4 each, with the help of semantic cues. After learning the first 16 figures, the participant recalls them three times, with distraction activity between each attempt (counting 20 to 1 backwards). The sum of each immediate free recall is called sum of attempts. It ranges from 0 (the participant does not recall any of the 16 figures in three attempts) to 48 (the participant recalls all the figures). We used this score as a measurement of episodic memory for the primary outcome.

The total raw score on the free recall sum-of-attempts trial from the FCST at the 6 months of follow up will be subtracted by the same score at baseline, in the intervention and control groups. The mean difference in each group will be compared using a paired T-test.

Secondary outcome:

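### The primary analysis is a paired t-test with no pair named, and the protocol does not settle whether individuals, matched pairs or classes were randomised

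*SAP*

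**What the plan says.** SAP, Primary outcome: the 6-month free-recall sum "will be subtracted by the same score at baseline, in the intervention and control groups". Then: "The mean difference in each group will be compared using a paired T-test". This is the only inferential statement for the primary outcome. The Secondary outcome uses the same sentence for hippocampal–prefrontal connectivity and names age as a covariate without saying at which step it enters. Neither section mentions matched pairs, a rule for pairs that lose a member, or class.

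The protocol describes allocation in three ways:

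- Participants: "pair matching with the 120 participants dividing them into two clusters paired for age, sex and baseline non-verbal intelligence", with literacy level as a further matching variable. Then: "within each pair, one cluster is randomized to receive the intervention (n=60), and the other cluster receives the placebo (n=60").
- Literacy training: "At baseline, participants will be randomized into four classes of 30", followed by "Two of the classes of 30 each will be the intervention group".
- Literacy training, on what the consent form explains: "participants will be randomly assigned to participate in the intervention or placebo group in the first 6 months".

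Both protocol sections expect 20% dropout and 96 completers. On dropouts: "Participants who drop out will be monitored by phone calls every three months and will be also reassessed after 6 months, if interested".

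**The concern.** A paired t-test is defined only once the pair is named. Here the pair could be two matched people in opposite arms. If no such pairs were formed, the arms are two independent groups and the named test does not apply to them. If classes were the randomised unit, neither an individual-level paired test nor a two-sample test gives a valid standard error.

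The SAP does not choose between these, and the protocol cannot be used to infer the choice. In Participants, the word cluster stands both for a group of 60 and for one member of a pair. Literacy training has people randomised into classes and never mentions matching. At stake are which participants enter the primary analysis, how precise it is, and whether its confidence interval matches the way the trial was allocated.

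**Working it through.** **Inputs from the documents.** 120 recruited, 60 per arm; 20% dropout; four classes of 30, two per arm.

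**Assumptions, because the documents give no value.** Two-sided 5%; a true difference of 0.5 SD of the change score; 12 dropouts per arm; no class effect; within-pair correlation of change ρ from 0 to 0.5; correlation r between baseline and 6-month scores from 0.5 to 0.8.

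**1. The plan's own figure.** 120 × 0.80 = 96 completers, 48 per arm. This reproduces. No power or sample-size figure is stated, so none can be checked.

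**2. Complete pairs, if 60 individual pairs exist and dropouts have no 6-month score.**

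| Dropout pattern | Complete pairs | Completers unused |
|---|---|---|
| Independent | 60 × 0.8 × 0.8 = 38.4 | 96 − 76.8 = 19.2 (20%) |
| Always both members | 60 − 12 = 48 | 0 |
| Never both members | 60 − 24 = 36 | 96 − 72 = 24 (25%) |

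Reassessing some dropouts would raise the number of complete pairs.

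**3. Power at 0.5 SD (noncentral t).**

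Two-sample test, 48 per arm: noncentrality 0.5 × √(48/2) = 2.45, df 94, power 68%.

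Paired test, 38 pairs: noncentrality 0.5 / √(2(1 − ρ)/38), df 37.

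| ρ | Noncentrality | Power |
|---|---|---|
| 0 | 2.18 | 56% |
| 0.2 | 2.44 | 66% |
| 0.3 | 2.61 | 72% |
| 0.5 | 3.08 | 85% |

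On variance alone the two tests tie when 2(1 − ρ)/38 = 2/48, so ρ = 1 − 38/48 = 0.21. The smaller df moves the tie in power to 0.23. The tie is at 0.02 with 48 pairs and 0.28 with 36.

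**4. If no individual pairs exist.** Step 3 reduces to the two-sample row. The named test has nothing to pair across arms.

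**5. If the class is the unit.** Four classes leave 2 df (critical t 4.30), or 1 df if classes are themselves paired (critical t 12.71).

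**6. Change score against ANCOVA.** With equal SD σ at both visits, the change score has variance 2σ²(1 − r) and the baseline-adjusted residual has σ²(1 − r²). The ratio is (1 + r)/2: 0.75 at r = 0.5 and 0.90 at r = 0.8. The noncentrality 2.45 becomes 2.45/√0.75 = 2.83 or 2.45/√0.90 = 2.58, so 68% power becomes 80% or 72%. Subtracting baseline is valid; it costs precision only.

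**7. Complete pairs against ANCOVA.** With 38 pairs, the complete-pair test overtakes ANCOVA on baseline alone when ρ exceeds 0.43 (r = 0.5) or 0.31 (r = 0.8). If ρ arises wholly through the matching variables (exact matching, linear effects), adjusting the change-score comparison for them in all completers gives variance 2(1 − ρ)/48 against 2(1 − ρ)/38.4 for pairs. The ratio is 38.4/48 = 0.80 in favour of adjustment.

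**The case against.** The strongest reply is that the two documents can be read together. Participants matches people on four variables and randomises within pairs, 60 to each arm, and the SAP then names a paired test. Sixty individual pairs with a paired test of change is a coherent design. The test drops incomplete pairs by construction, so it runs without a broken-pair rule. The two clusters may simply be the two arms, the classes may be delivery groups for people already allocated, and the sentence on random assignment reports consent wording. The paired test may also be the more powerful one, and reassessment of dropouts may leave fewer broken pairs than step 2 shows.

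Most of this stands. A reader might infer that the primary test cannot be run until someone makes a choice the SAP omits, or that the protocol proves incompatible randomisations. The documents do not support either inference: one reasonable reading gives a runnable, valid test, and the wording is unclear rather than demonstrably contradictory. Nor do they show that pairing loses power. A reader might also take the sentence as a before–after test within each arm. The SAP's sentence compares the arms' mean changes, so the point does not rest on that reading.

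The reply does not remove the gap. The SAP never mentions matched pairs, Literacy training describes allocation without them, and nothing says that the first description governs. ANCOVA is not needed for validity, and naming the pair or deleting the word paired would be a sufficient minimum. It is still the better choice, because it works with or without pairs and uses everyone with a 6-month score.

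**Conclusion.** The concern holds as an incompletely specified primary analysis that should be fixed before the data are analysed. It is not a demonstrated invalid test.

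- **Individual pairs exist:** the stated test is valid apart from any class effect, but rests on about 38 of 60 pairs (36 to 48 with 12 dropouts per arm, more if dropouts are reassessed). The effect on power can go either way, with break-even at a within-pair correlation of 0.23 for 38 pairs.
- **No individual pairs exist:** the stated test is the wrong one for two independent arms.
- **Classes or whole groups were randomised:** individual-level inference is not valid on either test.

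The counts rest on the plan's 20% dropout. The power figures rest on an assumed 0.5 SD, two-sided 5% and no class effect, none of which the documents give. The text leaves no doubt that the pair is unnamed; which allocation was carried out cannot be told from it.

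**What to change.** 1. Reconcile Participants with Literacy training in the protocol: state whether individuals, pairs or classes were randomised, and whether 60 individual pairs were formed.

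2. If individuals or pairs were randomised, replace the test sentence in the SAP's Primary outcome with:

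> The 6-month free-recall sum will be compared between randomised arms by ANCOVA adjusting for the baseline free-recall sum and the matching variables (age, sex, Beta-3, TOFHLA), in all randomised participants with a 6-month score, including those who stopped classes. The adjusted mean difference (intervention minus placebo) with 95% CI is the primary result.

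If pairs exist, add a complete-pair analysis as a sensitivity analysis and report the number of broken pairs.

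3. In the Secondary outcome, use the same model for each hippocampal seed, with baseline connectivity and age as covariates, and state where age enters.

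**Cost.** Two SAP sentences and one protocol clarification. No new data are needed, since every covariate is already planned at baseline. The downside is that, if within-pair correlation of change is high and does not come through the matching variables, the complete-pair test could be more precise.

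**Limit.** The individual-level confidence interval takes no account of shared classes, two per arm, and would not be valid if classes or whole groups were randomised. That needs separate handling, which this wording does not provide.

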**Cognitive evaluation:** Includes the MMSE, the Brief Cognitive Battery, and the Free and Cued Selective Reminding with Immediate Recall (FCSR-IR). The first two tests will assess global cognition and will be used as a screening for the presence of baseline cognitive impairment. The FCSR-IR includes a controlled learning phase, which provides the basis for encoding specificity and effective cued recall. The FCSR-IR Free Recall sum-of-attempts will be the proxy for episodic memory. We will also test other cognitive abilities than episodic memory such as non-verbal intelligence (Beta-3 test), attention (digit span), reading abilities (Human Frontier Science Program reading test), words and sentence repetition, rapid naming of colors, letters, numbers, and objects and verbal comprehension (Token test). Although scores for all tests described are known to be affected by literacy level, this effect will be accounted for because our participants will all have a low literacy level.

**Neuroimaging acquisition and analysis:** We will use the ADNI-3 protocol to acquire Diffusion tensor Imaging (DTI), resting-state functional MRI (rsfMRI), Fluid Attenuation Recovery and 3D-T1 images pre-and post-intervention in a 3T Siemens Verio scanner. For the rsfMRI analysis, a filter will be applied to attenuate noise frequencies of raw signal. We will then place a seed in the right and left hippocampus (HC) with an automated atlas that will be used to assess coherent blood oxygen level-dependent activity (BOLD) between this region and the ventral medial prefrontal cortex, corresponding to the HC-VMPFC intrinsic

functional connectivity (iFC). Both HC and VMPFC will be used in the region of interest (ROI) analyses, and ROI-averaged values for iFC and gray matter values will be calculated pre- and post-intervention.

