The intrinsic connectivity between the hippocampus and the prefrontal cortex will be measured using resting state functional MRI. The participants will undergo one MRI scan at baseline and one MRI scan at the 6 months follow up. The BOLD signal (blood oxygen level dependent) will be extracted as follows. First, a reference volume and its skull-stripped version will be generated using a custom methodology of fMRIPrep. Head-motion parameters with respect to the BOLD reference (transformation matrices, and six corresponding rotation and translation parameters) will be estimated. The estimated fieldmap will be then aligned with rigid-registration to the target EPI (echo-planar imaging) reference run. The field coefficients will be mapped on to the reference EPI using the transform. BOLD runs will be slice-time corrected to 1.44s (0.5 of slice acquisition range 0s-2.88s). The BOLD reference will be then co-registered to the T1 reference. Coregistration will be configured with six degrees of freedom. The three global signals will be extracted within the cerebral spinal fluid and the white matter, and the whole-brain masks. Additionally, a set of physiological regressors will be extracted to allow for component-based noise correction. Principal components will be estimated after high-pass filtering the preprocessed BOLD time-series. The confound time series derived from head motion estimates and global signals will be expanded with the inclusion of temporal derivatives and quadratic terms for each. The BOLD time-series will be resampled into standard space, generating a preprocessed BOLD run in a standard space. Age will be included as a covariate in this analysis.

A seed will be placed in each hippocampus (right and left) and the intrinsic functional connectivity, meaning the BOLD activity between each hippocampus and the prefrontal cortex will be calculated at baseline and at the 6 months of follow up. The intrinsic functional connectivity at 6 months will be subtracted from the baseline. The mean difference in each group will be compared using a paired T-test.

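### The SAP promises an age covariate for the connectivity outcome, but the only test it names, a paired t-test on change, has no term for age

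*SAP*

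**What the plan says.** Under Secondary outcome, the SAP describes the fMRI preprocessing at length and closes that paragraph with "Age will be included as a covariate in this analysis". The next paragraph defines connectivity for the right and left hippocampal seeds at baseline and 6 months, takes the difference, and names the test: "The mean difference in each group will be compared using a paired T-test". No other inferential method is given for this outcome.

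Under Primary outcome, the SAP uses the same test sentence, word for word, for episodic memory, with no covariate mentioned.

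The protocol (Neuroimaging acquisition and analysis) stops at the summary measures: "ROI-averaged values for iFC and gray matter values will be calculated pre- and post-intervention". It names neither a test nor an age term. Elsewhere it uses age in two ways. Age is an eligibility limit ("Inclusion criteria include any gender, age between 40 and 89 years old") and a matching factor ("pair matching with the 120 participants dividing them into two clusters paired for age, sex and baseline non-verbal intelligence", plus literacy level).

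**The concern.** A covariate needs a model with a place for it. A paired t-test estimates one quantity, the mean of a set of differences. It is an intercept-only model on those differences, whether each pair is two scans of one person or two matched people. Taken together, the two SAP sentences promise an adjustment that the named test cannot make.

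The analysis is under-specified, not impossible. Age could be regressed out of the change scores first, entered as a within-pair age difference, or entered in a regression across all completers. The SAP does not choose, so the choice may be made after the data are seen. The routes can also differ in who is analysed and how precise the result is.

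**Working it through.** **1. Could the age sentence belong to another step?** The steps before it (head motion, field correction, slice timing, coregistration, confound series) are carried out scan by scan. Age is constant within a scan, so an intercept plus an age column has rank 1 and age adds nothing. It can act only across participants, and no across-participant model is named. Nor can the t-test sentence be shorthand for an adjusted comparison, because the identical sentence serves the primary outcome, which has no covariate.

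**2. The protocol's own figure.** 120 × (1 − 0.20) = 96, which agrees with "Thus, the final sample is expected to have 96 individuals". The documents give no alpha, power, effect size or SD for this outcome. The figures below therefore assume a two-sided 5% test.

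**3. How much does age in or out matter?** Simulation with no treatment effect: 16 scenarios of 20,000 runs, Monte Carlo error about 0.15 percentage points. Assumed: 60 one-to-one pairs, ages uniform over 40–89, matching within 2 or 5 years, 20% independent dropout, retest correlation 0.3 or 0.6, age-change correlation 0 or 0.3, within-pair correlation 0 or 0.2.

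| Participants | Each method alone | Smaller p, age in or out |
|---|---|---|
| Complete pairs | 4.8–5.3% | 5.4–6.0% |
| All completers | 2.6–5.1% | 3.4–5.5% |

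The low values in the second row arise at within-pair correlation 0.2, because the matching is ignored. Putting age in or out changes the sampling SE of the arm estimate by less than 2%. On complete pairs the estimate itself moves by about 0.17 SE (root mean square). That shift is nearly the same whether or not age is related to change, so it is mostly the noise of fitting one more coefficient.

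**4. What does baseline connectivity add?** Let r be the retest correlation and σ² the common variance.

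- Variance of a change score: 2σ²(1 − r).
- Residual variance after adjusting for baseline: σ²(1 − r²).
- SE ratio: √[(1 + r)/2].
- r = 0.3: √0.65 = 0.81. r = 0.6: √0.80 = 0.89.

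The simulated ratios were 0.80–0.91.

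**5. Who is analysed?** This depends on what is paired. If it is two scans of one person, all 96 completers count. If it is one-to-one matched people, with 120 × 0.20 = 24 dropouts who have no second scan:

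- every dropout in a different pair: 60 − 24 = 36 complete pairs (72 people);
- dropouts always both members of a pair: 60 − 12 = 48 pairs (96 people);
- independent dropout: 60 × 0.8² = 38.4 pairs (76.8 people), leaving 96 − 76.8 = 19.2 completers unused.

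For independent dropout and within-pair correlation ρ, the SE of an unpaired model on 48 per arm, relative to the paired test, is √[38.4 / (48(1 − ρ))]. This is 0.89 at ρ = 0 and 1.00 at ρ = 0.2. Using all completers therefore helps most when matching explains little. With baseline connectivity included as well, the simulated SE was 0.74–0.91 of that of the complete-pairs paired t-test.

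**6. The cost of ignoring pairs.** At ρ = 0.2, the true variance of the unpaired estimate is about 1 − 0.8 × 0.2 = 0.84 of the variance the model reports. The effective critical value is 1.96/√0.84 = 2.14, which gives about 3.2% rejection, in line with the simulated 3–4%.

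**The case against.** The strongest reply is that this is a wording gap in a secondary outcome, in randomised arms already matched on age, and that the numerical harm is slight even for an analyst who always keeps the smaller p-value. That stands, and it sets the severity. It does not close the gap: matching is a design feature and not a covariate, and the SAP never says that its pairs are the matched pairs.

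A reader might infer that the missing age model inflates false positives to 6.1–7.3%. That range appears only if the analyst may also choose between a paired t-test on complete pairs and an age-adjusted regression on all completers. It comes from the undefined pairing, which the primary outcome shares, and it assumes one-to-one matching. The documents do not establish such pairs: the protocol speaks of two clusters under Participants, while under Literacy training it says "At baseline, participants will be randomized into four classes of 30". The pair counts above carry the same condition. They also assume that dropouts have no 6-month scan, although the protocol lets those who are interested be reassessed.

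A reader might also make something of the direction of change. Read literally, the SAP takes baseline minus 6 months for connectivity and the reverse for memory. This flips the sign but leaves the size and the two-sided p-value unchanged, so it is editorial.

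Finally, it is fair to say that a model with baseline connectivity does more than repair the age sentence. The gain comes from baseline and from the participants kept, not from age. The case for it is that it settles the age question and improves precision with data already collected.

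**Conclusion.** The point holds as a minor one. The SAP calls for age adjustment of the connectivity outcome, names a test that cannot provide it, and gives no model that could. Leaving age in or out has little effect: at most about 6% false positives under selective reporting, given the simulation assumptions. The larger benefit of a correction is an SE about 0.8 to 0.9 of the change-score value, which rests on an assumed retest correlation of 0.3 to 0.6. Keeping all completers adds to this only if the pairs are one-to-one. The documents do not support a claim that the analysis is impossible, or that the missing age model on its own materially distorts the trial's error rate.

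**What to change.** Replace the age sentence and the paired t-test for this outcome with:

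*For each hippocampal seed (right and left) separately, 6-month hippocampus-prefrontal connectivity will be compared between arms by a linear model with arm, baseline connectivity and age, in all participants with both scans. The result is the adjusted difference, intervention minus control, with 95% CI.*

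Reconcile the target region at the same time: the SAP refers to the prefrontal cortex, the protocol to its ventral medial part. As an editorial change, describe change as 6 months minus baseline, as for the primary outcome.

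The cost is a few sentences and no new data. There are two downsides. The method then differs from the primary outcome's test. Without a pair term it is slightly conservative if outcomes correlate within pairs (about 3–4% rejection at an assumed correlation of 0.2). A pair term can be added if pair membership was recorded, which the documents do not say. Clustering by class is a separate matter that this wording does not address.

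Minimum alternative: delete the age sentence and state what is paired with what.
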